## 2) Allergies and Adverse Drug Reaction

- a) History of any significant treatment allergy (such as anaphylaxis or hepatotoxicity) to prior anti-cancer immune-modulating therapies (eg, checkpoint inhibitors and T-cell co-stimulatory antibodies).
- b) History of allergy or hypersensitivity to study treatment components.

## 3) Other Exclusion Criteria

- a) Prisoners or participants who are involuntarily incarcerated. Note: Under certain specific circumstances, and only in countries where local regulations permit, a person who has been imprisoned may be included or permitted to continue as a participant. Strict conditions apply, and BMS approval is required.
- b) Participants who are compulsorily detained for treatment of either a psychiatric or physical (eg, infectious disease) illness

Eligibility criteria for this study have been carefully considered to ensure the safety of the study participants and that the results of the study can be used. It is imperative that participants fully meet all eligibility criteria.

### 6.3 Lifestyle Restrictions

Not applicable. No restrictions are required.

### 6.4 Screen Failures

Screen failures are defined as participants who consent to participate in the clinical study but are not subsequently randomized. A minimal set of screen failure information is required to ensure transparent reporting of screen failure participants to meet the Consolidated Standards of Reporting Trials publishing requirements and to respond to queries from regulatory authorities. Minimal information includes date of consent, demography, screen failure details, eligibility criteria, and any serious AEs.

#### 6.4.1 Retesting During Screening

**Participant Re-enrollment:** This study permits the re-enrollment of a participant that has discontinued the study as a pretreatment failure (ie, participant has not been randomized or has not been treated). If re-enrolled, the participant must be re-consented.

Retesting of laboratory parameters and/or other assessments within any single Screening Phase will be permitted (in addition to any parameters that require a confirmatory value).

The most current result prior to randomization is the value by which study inclusion will be assessed, as it represents the participant's most current, clinical state.

Laboratory parameters and/or assessments that are included in [Table 2-1](#), Screening Procedural Outline, may be repeated in an effort to find all possible well-qualified participants. Consultation

with the BMS Medical Monitor (or designee) may be needed to identify whether repeat testing of any particular parameter is clinically relevant.

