    - vii) Serum creatinine  $\leq 1.5 \times$  institutional ULN or creatinine clearance (CrCl)  $\geq 40$  mL/min (measured using the Cockcroft-Gault formula below):
$$\text{Female CrCl} = \frac{(140 - \text{age in years}) \times \text{weight in kg} \times 0.85}{72 \times \text{serum creatinine in mg/dL}}$$
$$\text{Male CrCl} = \frac{(140 - \text{age in years}) \times \text{weight in kg} \times 1.00}{72 \times \text{serum creatinine in mg/dL}}$$
  - m) Participants must be able to comply with restrictions and prohibited activities/treatments listed in [Section 7.7.1](#).
  - n) Participant re-enrollment: This study permits the re-enrollment of a participant who has discontinued the study as a pretreatment failure (eg, participant has not been treated). If re-enrolled, the participant must be re-consented.
  - o) Participants must allow a tumor biopsy at baseline and on study.
    - i) Participants who do not have accessible or suitable lesions are not eligible.
    - ii) For participants whose pretreatment biopsy yields inadequate tissue quantity or quality (as determined by a pathologist in the central laboratory), re-biopsy is permitted.
    - iii) The solid tumor tissue specimen must be a core-needle, biopsy or an excisional or incisional biopsy. Fine-needle biopsies and drainage of pleural effusions with cytospins

are not considered adequate for biomarker review and randomization. Biopsies of bone lesions that do not have a soft tissue component or decalcified bone tumor samples are also not acceptable.

(1).Punch biopsies are acceptable as long as adequate tumor material is provided.

iv) The biopsy at progression of disease after treatment on any track may function as the pretreatment biopsy for subsequent treatment on Track 2.

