### **7.2 Method of Treatment Assignment**

This is an open-label study. All participants will be centrally randomized using an IRT. Before the study is initiated, each user will receive log-in information and directions on how to access the IRT.

Specific study treatments are listed in each FRACTION-Gastric Cancer Sub-Protocol. Study treatment will be dispensed at the study visits, as listed in the On-treatment Procedural Outline(s) in each FRACTION-Gastric Cancer Sub-Protocol.

All participants must be assigned a patient identification number (PID) upon providing a signed IRB/IEC-approved written informed consent. During the screening visit, the investigative site will utilize the IRT for enrollment and receive a 5-digit PID designated by BMS that will be unique across all sites. Enrolled participants, including those not dosed, will be assigned sequential PIDs starting with [REDACTED]. The PID will ultimately be composed of the site number and participant number. For example, the first participant screened (eg, enrolled) at Site Number 1 will have a PID of [REDACTED]. The following information is required for enrollment:

- Date of obtaining informed consent
- Date of birth

- Gender at birth
- Anti-PD-1, anti-PD-L1, or anti-CTLA-4 treatment experience (see [Section 5.1.3.1](#))

Once enrolled in the IRT, participants who meet all eligibility criteria will be ready to be randomized through the IRT. The following information is required for randomization:

- Participant number
- Date of birth

Randomization participant schedules will be generated and maintained by the IRT vendor. At the conclusion of the trials, BMS will receive copies of all generated participant schedules from the vendor. Because of the nature of the study design, limited early access to the randomization information will be granted to the study team to facilitate early analyses for internal decision making (early termination of study treatment arm, etc).

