### **7.3 Blinding**

This is an open-label study; blinding procedures are not applicable.

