## 10.2 Populations for Analyses

For purposes of analysis, the following populations are defined:

Population	Description
Enrolled	All participants who sign informed consent
Randomized	All participants who are randomized to any study treatment arm of any track in this study
Treated	All participants who are randomized and take at least 1 dose of study treatment
PK	All treated participants who have evaluable concentration time data
Immunogenicity	All treated participants who have available immunogenicity assessment data
Biomarker	All treated participants who have available biomarker data

Population	Description
Response-evaluable	All treated participants with measurable disease and 1 of the following: 1) at least 1 postbaseline tumor measurement, 2) clinical progression, or 3) death

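### Re-enrolment is open to participants already randomized but not treated, and the master protocol does not say that they keep their first assignment

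*Combined protocol and SAP*

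**What the plan says.** Section 6.4 defines screen failures as "participants who consent to participate in the clinical study but are not subsequently randomized". The re-enrolment rule directly below it is wider. Section 6.4.1 admits a participant who has "discontinued the study as a pretreatment failure (ie, participant has not been randomized or has not been treated", and inclusion criterion 2n admits one who "has discontinued the study as a pretreatment failure (eg, participant has not been treated". The one condition attached is this: "If re-enrolled, the participant must be re-consented".

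On assignment, Section 7.2 states: "This is an open-label study. All participants will be centrally randomized using an IRT". Section 7.3 confirms that there is no blinding. Table 2-1 lets randomization precede the first dose by up to 7 days, and by longer in limited circumstances after discussion with the medical monitor. Section 9.2.1 foresees people who are randomized and never treated, since it sets a 30-day SAE collection period for them.

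Section 7.2 deals with a second randomization number only for re-randomization in Track 2. It refers detailed randomization instructions to a separate manual and allocation ratios to the sub-protocols.

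Section 10.2 defines the Treated population as "All participants who are randomized and take at least 1 dose of study treatment", and Section 10.3.1 makes it the primary efficacy population. For Track 1, Section 10.3.1 plans a descriptive odds ratio and ORR difference, and PFS and OS hazard ratios, against nivolumab plus ipilimumab.

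**The concern.** Read together, these provisions leave open a route by which the arm in which a participant is analysed depends on that participant's reaction to a known assignment. Someone drawn to the control could decline before dosing, consent again, re-enter the IRT and draw another arm. Having received no checkpoint inhibitor in the study, this person would still be eligible for Track 1. The declined assignment would not appear in the Treated population.

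If people who decline and come back differ in prognosis from those who accept, the arms are no longer comparable. At stake are the ORR of each arm, which is set against the Simon boundaries, and the descriptive Track 1 comparison. The comparison has some weight, because Sections 10.1 and 10.1.1 say that the relative performance of the arms is reviewed before an arm is stopped or continued.

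**Working it through.** **What the text settles.** The *or* in Section 6.4.1 covers the randomized, undosed participant, and criterion 2n does not exclude one. Section 7.2 lists the information needed to enrol (consent date, birth date, gender, prior checkpoint-inhibitor exposure) and to randomize (participant number, birth date). Neither list includes a previous assignment. Section 5.1.3.1 has its own route for participants who overrun the 28-day screening window, so that need does not explain the wider wording.

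**The plan's own figures.** The Track 1 Simon design (4/19, 15/54) declares efficacy with probability Σ b(x; 19, p) × P(X₂ ≥ 16 − x), summed over x = 5 to 19, with X₂ binomial (35, p). This gives 0.048 at p = 20% and 0.904 at p = 40%. The chance of stopping at Stage 1 under 20% is 0.673, and expected n is 30.4 and 51.6. These agree with Table 10.1-1 and Section 10.1.1 and are not in dispute.

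**Effect on the between-arm difference.** The documents give no refusal rate, no prognosis for refusers and no allocation ratio, so these inputs are assumptions: 100 randomized per arm (1:1), identical drugs, 10% who would refuse control, ORR 40% in refusers and 20% in others. Each arm then holds 90 others (18 responses) and 10 people of the refusing type.

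| Treated set | Control | Experimental | Difference (points) | Change due to re-enrolment |
|---|---|---|---|---|
| No re-enrolment; refusers leave untreated | 18/90 = 20.0% | (18 + 4)/100 = 22.0% | 2.0 | none |
| Redraw until experimental | 18/90 = 20.0% | (18 + 8)/110 = 23.6% | 3.6 | +1.6 |
| One redraw; those drawing control again leave | 18/90 = 20.0% | (18 + 6)/105 = 22.9% | 2.9 | +0.9 |
| One redraw; control accepted if drawn | (18 + 2)/95 = 21.1% | (18 + 6)/105 = 22.9% | 1.8 | −0.2 |

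With 5% refusers at ORR 30%, the difference is 0.5 points with no re-enrolment (19/95 against 20.5/100). It is 0.95 with full redraw (22/105 = 20.95%) and 0.73 with one redraw where the rest leave (21.25/102.5 = 20.73%). Re-enrolment adds 0.45 and 0.23 points. If refusers have the same ORR as others, every entry is 20% and there is no bias.

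**Effect on the experimental arm's Simon rule.** Set the overall ORR at the null value of 20%, with 10% refusers at 40%, so that the others have (0.20 − 0.10 × 0.40)/0.90 = 17.8%. With no re-enrolment the experimental arm stays at 20.0%, with a false positive probability of 4.8%. One redraw gives (20 + 5 × 0.40)/105 = 20.95% and 6.9%. Full redraw gives (20 + 10 × 0.40)/110 = 21.8% and 9.2%.

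**Analysis by first randomized arm.** In the full-redraw case of the table, the participants first drawn to control give (18 + 4)/100 = 22.0%, against 22.0% for experimental, so the false difference disappears. Where refusers leave untreated, part remains: with one redraw and the rest leaving, (18 + 2)/95 = 21.1% against 22.0%, or 0.9 points.

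**The case against.** The strongest objection is that no section grants a new draw. That step is inferred from the absence of a restriction. The PID is the participant's primary identifier, the randomization instructions are in a manual that is not available here, and the IRT may well recognise an existing assignment. This stands: a reader might infer that the protocol entitles a re-enrolled participant to a fresh randomization, and the text does not say so. It does expressly open re-enrolment to people already randomized, and it is silent on what happens to their assignment. That gap belongs to the master protocol whatever the IRT does.

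A reader might also call this a failure of allocation concealment. It is not. Central randomization still hides the next assignment, and the selection comes after the assignment is known.

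A third tempting reading puts the whole 3.6 points down to re-enrolment. The table does not support that. The Treated population drops undosed refusers in any case, and this alone produces 2.0 points.

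It is also fair to say that repeated redraws are hard to achieve in practice, given the screening windows, the centrally confirmed biopsy and the life-expectancy criterion. In addition, the Track 1 comparison is descriptive, Simon decisions are made per arm and serve as guidelines, and Amendment 06 records early closure. These points limit the consequence and shift the useful action from rewording to checking the data. They do not remove the gap, because Amendment 06 left the re-enrolment wording in both places.

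**Conclusion.** The point holds as a gap in the assignment rules with a modest possible effect. The documents permit re-enrolment after randomization in an open-label trial and do not protect the first assignment. Whether any participant actually drew a second arm cannot be told from them.

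Under the assumptions above, re-enrolment adds at most about 1.6 points to a false ORR difference that is already 2.0 points. It adds 0.9 if there is a single redraw and those drawing control again leave, and it slightly narrows the gap, to 1.8, if they accept control. It adds nothing if refusers have average prognosis. The inflated false positive probability in the experimental arm (from 4.8% to 6.9% or 9.2%) rests on the same unsupported inputs.

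One might conclude that no choice of analysis set can repair the problem. That goes too far: grouping by first randomized arm restores the randomized comparison as far as those participants were eventually treated and followed. When the drugs differ, that comparison mixes treatments for those who changed arm, so it serves as a sensitivity analysis.

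**What to change.** - In Section 6.4.1 and criterion 2n, limit re-enrolment to participants not yet randomized. Alternatively, if a randomized, untreated participant may be screened again (for example after a delayed test), state that the IRT retains the PID and the original assignment and makes no new draw. If the IRT manual already does this, say so in the master protocol.
- List every participant with more than one initial randomization, with each assigned arm and the reason for not being treated. If there are none, report that.
- Repeat the Track 1 ORR, PFS and OS comparison with each participant in the first randomized arm, and state the time origin for PFS and OS, which Section 10.3.1 counts from first dose. Report randomized, never-treated participants by first assigned arm, because this analysis cannot recover their outcomes.

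As the trial is closing early, the listing and the first-assignment analysis are the main practical steps. The rewording matters if enrolment continues or the text is reused. The cost is one sentence in two places, an IRT rule, one listing and one extra analysis. The downside is small: a few participants who reject their first assignment could not return for another.

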## **7 TREATMENT**

Study treatment is defined as any investigational treatment(s), marketed product(s), placebo, or medical device intended to be administered to a study participant according to the study randomization or treatment allocation.

Study treatment includes both Investigational [Medicinal] Product (IP/IMP) and Non-IP/Non-IMP and is described in each FRACTION-Gastric Cancer Sub-Protocol.

An IP, also known as IMP in some regions, is defined as a pharmaceutical form of an active substance or placebo being tested or used as a reference in a clinical study, including products already with a marketing authorization but used or assembled (formulated or packaged) differently from the authorized form, used for an unauthorized indication, or used to gain further information about the authorized form.

Other medications used as support or escape medication for preventive, diagnostic, or therapeutic reasons, as components of the standard of care for a given diagnosis, may be considered as non-IPs.

### **7.1 Treatments Administered**

Other treatments administered as part of the study that are critical to claims of efficacy (eg, background treatment and rescue medications) will be considered study treatment. A table describing the study treatments and dosage information is provided in each FRACTION-Gastric Cancer Sub-Protocol.

### **7.2 Method of Treatment Assignment**

This is an open-label study. All participants will be centrally randomized using an IRT. Before the study is initiated, each user will receive log-in information and directions on how to access the IRT.

Specific study treatments are listed in each FRACTION-Gastric Cancer Sub-Protocol. Study treatment will be dispensed at the study visits, as listed in the On-treatment Procedural Outline(s) in each FRACTION-Gastric Cancer Sub-Protocol.

All participants must be assigned a patient identification number (PID) upon providing a signed IRB/IEC-approved written informed consent. During the screening visit, the investigative site will utilize the IRT for enrollment and receive a 5-digit PID designated by BMS that will be unique across all sites. Enrolled participants, including those not dosed, will be assigned sequential PIDs starting with [REDACTED]. The PID will ultimately be composed of the site number and participant number. For example, the first participant screened (eg, enrolled) at Site Number 1 will have a PID of [REDACTED]. The following information is required for enrollment:

- Date of obtaining informed consent
- Date of birth

- Gender at birth
- Anti-PD-1, anti-PD-L1, or anti-CTLA-4 treatment experience (see [Section 5.1.3.1](#))

Once enrolled in the IRT, participants who meet all eligibility criteria will be ready to be randomized through the IRT. The following information is required for randomization:

- Participant number
- Date of birth

Randomization participant schedules will be generated and maintained by the IRT vendor. At the conclusion of the trials, BMS will receive copies of all generated participant schedules from the vendor. Because of the nature of the study design, limited early access to the randomization information will be granted to the study team to facilitate early analyses for internal decision making (early termination of study treatment arm, etc).

Each participant who is randomized will be assigned a unique randomization number. This is not the primary identifier for the participant, but is used for the randomization schedule. The primary identifier will be the PID described above, for use on the case report form (CRF) and source documents. A participant being re-randomized in Track 2 will be assigned a different randomization number but will retain the same PID. Randomization numbers will be assigned using a Central Randomization System in the order in which participants qualify for study treatment, not in the order of study enrollment. Randomization ratios within each track will be specified in each FRACTION-Gastric Cancer Sub-Protocol. If, within a given track, study treatment arms from more than 1 FRACTION-Gastric Cancer Sub-Protocol within the FRACTION-Gastric Cancer Master Protocol are simultaneously open to enrollment, then a new participant could be assigned to any of the open study treatment arms. In Track 1, participants will be randomized to newly added study treatment arms/study treatments (through FRACTION-Gastric Cancer Sub-Protocols) in a ratio specified in each new FRACTION-Gastric Cancer Sub-Protocol. New randomization schedules for new FRACTION-Gastric Cancer Sub-Protocols will be generated. If accrual for current FRACTION-Gastric Cancer Sub-Protocols is still ongoing, participants will be allocated to the existing randomization schedule or new randomization schedule based on a pre-specified allocation ratio. Details of allocation ratio will be specified in the new FRACTION-Gastric Cancer Sub-Protocol. In Track 2, participants will be randomized to existing study treatment arm/study treatments and newly added study treatment arm/study treatments with equal probability.

Pre-specified study treatment arm caps (according to Simon 2-stage [optimal] design) will be utilized to control the accrual for each study treatment combination arm under different tracks (Tracks 1 and 2). The cap for the nivolumab in combination with ipilimumab control arm under Track 1 will be set equal to the largest cap among its corresponding experimental arms. In the event that 1 or more participants go off study without being evaluable for response (ie, with no post-baseline tumor measurements and no evidence of clinical progression or death due to disease progression), the enrollment cap for that study treatment arm may be correspondingly raised if

needed to ensure that a sufficient number of evaluable participants are available for decision making according to the Simon 2-stage (optimal) design. If the decision is made to close any study treatment arm for safety concerns, the cap for that study treatment arm will be reduced to the current number of participants already randomized. Accrual will be stopped immediately. Enrollment caps to Track 2 based on new participants or re-randomized participants are described in [Section 10.1.2](#).

Specific instructions for randomization into the Central Randomization System will be provided in a separate manual.

### **7.3 Blinding**

This is an open-label study; blinding procedures are not applicable.

### **7.4 Dosage Modification**

Specific dosing and treatment regimens for each FRACTION-Gastric Cancer study treatment combination and/or nivolumab in combination with ipilimumab are outlined in each FRACTION-Gastric Cancer Sub-Protocol.

#### **7.4.1 Dose Reductions and Delays and Criteria to Resume Dosing**

Tumor assessments for all participants should continue as per protocol **even if dosing is delayed**.

Guidelines for dose reductions and delays due to toxicity and for resuming study treatment for each FRACTION-Gastric Cancer study treatment combination are provided in the FRACTION-Gastric Cancer Sub-Protocols.

